1 FLOW CHARTS

1.1 GRAPHICAL STUDY DESIGN

1.2 TREATMENT SCHEMA

[figure not shown]
Figure 2 - Treatment schema of TED14095

(IC: Informed Consent form signed, R: Registration, DLT: Dose Limiting Toxicity, EoT: End of Treatment, FUV: Follow-up Visit)

[figure not shown]
1.3 DESIGN DIAGRAM

Figure 3 - Dose escalation design for Cohort 1 (Initial dose level)

Abbreviations: DLT = Dose-Limiting Toxicity; MAD = Maximum Administered Dose

Figure 4 - Dose escalation design for Cohort 2 (global recommended dose level)

1.4 STUDY FLOWCHART - PHASE I PART

Phase I Part	Screening/ Baseline ²	Cycle 1 ³						Subsequent Cycles ^{3, 36}		End-of-Treatment	Follow-up
Evaluation ¹	D-21 to D-1	D1	D2	D3	D4	D8 ⁴	D15 ⁴	D22 ⁴	D1 ⁴	D15 ⁴	30 days (+/- 7 days) after last IMP administration
Eligibility criteria & Informed consent ⁵	X								Cycle 2 only ⁵		60 days (+/- 7 days) after last IMP administration and subsequent follow-up
Demography & Medical/surgical & Disease History ⁶	X										
Hospitalization ⁷		(X)	(X)	(X)	(X)	(X)					
Patient Registration		X ⁸									
Isatuximab Administration		X				X	X	X	X	X	
Isatuximab Safety Labs ⁹		(X)				(X)	(X)	(X)	(X)	(X)	
Cytokines		X									
Physical Examination ¹⁰	X	X				X	X	X	X	Cycle 2,3 only	X
Performance Status (ECOG)	X	X							X		X
Height	X										
Body weight	X	X				X	X	X	X	X	X
Vital Signs (HR, Temperature, RR, BP) ¹¹	X	X				X	X	X	X	X	X
12-Lead ECG, 2D Echocardiogram or MUGA ¹²	X										
Hematology ¹³	X	X ¹⁴				X	X	X	X	X	X
Serum Chemistry ¹⁵	X	X ¹⁴				X	X	X	X	X	X
Coagulation (PT/INR, aPTT) ¹⁶	X										
Urinalysis ¹⁷	X	X ¹⁴				X		X	X	X	
Pregnancy Test ¹⁸ (Within 7 days prior to Day 1)	X							X		X	
HIV-Ab, HBs-Ag, HBc-Ab, HBs-Ab HCV-Ab Tests ¹⁹	X										
Myeloma-specific Lab Tests ²¹	X	X ¹⁴						X		X	(X) ²³
Extramedullary Disease ²²	X							(Every 12 weeks)	(X)	(X)	(Every 12 weeks) ²³

Phase I Part	Screening/ Baseline ²	Cycle 1 ³						Subsequent Cycles ^{3, 36}		End-of-Treatment	Follow-up
Evaluation ¹	D-21 to D-1	D1	D2	D3	D4	D8 ⁴	D15 ⁴	D22 ⁴	D1 ⁴	D15 ⁴	30 days (+/- 7 days) after last IMP administration
Skeletal Survey and Chest X-ray ²⁴	X										60 days (+/- 7 days) after last IMP administration and subsequent follow-up
Isatuximab PK plasma samples (See PK flow chart)		X	X	X	X	X	X	X	X	X	
Immunogenicity (ADA) ²⁵		X				X	X	X	X	X	X
Soluble CD38 (PB) ²⁶		X									
Bone Marrow Aspiration and/or Biopsy ²⁷	X	(If CR is suspected)									
MRD assessment (BM) ²⁸	X	(If CR is suspected)									
CD38 Receptor Density (BM) ²⁹	X										
Cytogenetics/ FISH (BM) ³⁰	X										
Immune phenotyping (BM) ³¹	X										
Immune phenotyping (PB) ³²		X						X (C3 only)		X	
Immune genetic determinants (PB) ³³		X									
Survival Status											X ³⁴
New Anticancer Therapy											X
AE/ SAE Reporting ³⁵		Continuously throughout the study period									
Prior/ Concomitant Medication		Continuously throughout the study period									

(PB): Peripheral Blood sample, (BM): Bone Marrow sample

1.5 STUDY FLOWCHART - PHASE II PART

Phase II Part	Screening/ Baseline ²	Cycle 1 ³						Subsequent Cycles ^{3, 36}		End-of-Treatment	Follow-up
Evaluation ¹	D-21 to D-1	D1	D2	D3	D4	D8 ⁴	D15 ⁴	D22 ⁴	D1 ⁴	D15 ⁴	30 days (+/- 7 days) after last IMP administration
Eligibility criteria & Informed consent ⁵	X										60 days (+/- 7 days) after last IMP administration and subsequent follow-up
Demography & Medical/surgical & Disease History ⁶	X										
Patient Registration		X ⁸									
Isatuximab Administration		X				X	X	X	X	X	
Isatuximab Safety Labs ⁹		(X)			(X)	(X)	(X)	(X)	(X)	(X)	
Physical Examination ¹⁰	X	X			X	X	X	X	Cycle 2,3 only	X	
Performance Status (ECOG)	X	X						X		X	
Height	X										
Body weight	X	X			X	X	X	X	X	X	
Vital Signs (HR, Temperature, RR, BP) ¹¹	X	X			X	X	X	X	X	X	
12-Lead ECG, 2D Echocardiogram or MUGA ¹²	X										
Hematology ¹³	X	X ¹⁴			X	X	X	X	X	X	
Serum Chemistry ¹⁵	X	X ¹⁴			X	X	X	X	X	X	
Coagulation (PT/INR, aPTT) ¹⁶	X										
Urinalysis ¹⁷	X	X ¹⁴			X		X	X	X	X	
Pregnancy Test ¹⁸ (Within 7 days prior to Day 1)	X						X			X	
HIV-Ab, HBs-Ag, HCb-Ab, HBs-Ab HCV-Ab Tests ¹⁹	X							X ²⁰			
Myeloma-specific Lab Tests ²¹	X	X ¹⁴					X		X	(X)	²³
Extramedullary Disease ²²	X							(Every 12 weeks)	(X)	(Every 12 weeks)	²³

Phase II Part	Screening/ Baseline ²	Cycle 1 ³						Subsequent Cycles ^{3, 36}		End-of-Treatment	Follow-up
Evaluation ¹	D-21 to D-1	D1	D2	D3	D4	D8 ⁴	D15 ⁴	D22 ⁴	D1 ⁴	D15 ⁴	30 days (+/- 7 days) after last IMP administration
Skeletal Survey and Chest X-ray ²⁴	X										60 days (+/- 7 days) after last IMP administration and subsequent follow-up
Isatuximab PK plasma samples (See PK flow chart)		X				X	X	X	X	X	
Immunogenicity (ADA) ²⁵		X				X	X	X		X	X
Soluble CD38 ²⁶		X									
Bone Marrow Aspiration and/or Biopsy ²⁷	X	(If CR is suspected)									
MRD assessment (BM) ²⁸	X	(If CR is suspected)									
CD38 Receptor Density (BM) ²⁹	X										
Cytogenetics/FISH (BM) ³⁰	X										
Immune phenotyping (BM) ³¹	X										
Immune phenotyping (PB) ³²		X						X (C3 only)		X	
Immune genetic determinants (PB) ³³		X									
Survival Status											X ³⁴
New Anticancer Therapy											X
AE/ SAE Reporting ³⁵		Continuously throughout the study period									
Prior/ Concomitant Medication		Continuously throughout the study period									

(PB): Peripheral Blood sample, (BM): Bone Marrow sample

1.6 FOOTNOTES FOR STUDY FLOWCHARTS

1. Evaluation: Assessments to be performed prior to study drug administration unless otherwise indicated. Results should be reviewed by the Investigator.
2. If the patient cannot be registered within 21 days of informed consent, the same patient may be re-screened after discussion with the sponsor, provided that there are no persisting safety concerns for patient's study participation. The informed consent form will have to be re-signed by the re-screened patient before starting re-screening procedures. New patient number will be given for the re-screened patients.
3. Cycle: A cycle is 28 days.
4. Allowance for Day 8, Day15 and Day 22 at first cycle is +/- 2 days. Allowance for Day 1 and Day15 at subsequent cycles are +/- 3 days.
5. The ICF should be signed before any study-related procedures or tests are initiated.
All patients who participated in Phase I part and is going to continue study treatment after completing Cycle 1 must sign a second ICF before commencing IMP administration in Cycle 2 Day1.
6. Demography: Includes date of birth, gender and race.
Medical/Surgical History: Includes relevant history of previous/associated pathologies other than multiple myeloma.
Disease History: Includes date of initial diagnosis of symptomatic MM, subtype, stage, previous anti-MM therapy (drug name by line of therapy, start and end date of administration, reason for discontinuation, best response and date of progression/relapse), disease status at inclusion (refractory to last IMiD or PI included therapy). In addition, results of additional procedures (such as karyotype, FISH, etc) performed as part of standard of care to assess the current disease status may also be collected. A patient card will be provided to the patient indicating he/she is receiving an anti-CD38 treatment and the site will notify its blood bank that the patient is receiving an anti-CD38 treatment.
7. Hospitalization: Day 1 through the entire day of the 3rd infusion (Day 15) hospitalization is recommended. Hospitalization will be expanded to the entire first cycle of the study treatment (ie. DLT observation period), if the investigator and the study committee judged appropriate.
8. Registration process can be completed in Day -1 however all eligibility criteria should be re-confirmed by investigators in Day 1 before IMP administration.
9. Isatuximab Safety Labs: Should a isatuximab infusion associated reaction of Grade ≥ 2 occur, additional blood sampling during the AE is required for analysis of markers of potential tumor lysis syndrome (uric acid, lactate dehydrogenase [LDH], BUN, creatinine, potassium, phosphate, ionized or corrected calcium).
10. Physical Examination: Consists of examination of major body systems including neurological, digestive, extramedullary myeloma localizations, respiratory, hepatomegaly, splenomegaly, lymphadenopathy. Only clinically relevant findings will be reported in the electronic case report form (e-CRF) as AEs.
11. Vital Signs: Heart rate (HR), temperature, respiratory rate (RR), blood pressure (BP) to be taken pre-infusion, mid-infusion (when half the volume is administered), and end-infusion on days of investigational medicinal product (IMP) administration. If the infusion rate changes because of an infusion-associated reaction, vital signs should be monitored every hour and at the end of the infusion.
12. 12-Lead ECG, 2-D Echocardiogram or Multigated Acquisition (MUGA): To be performed at screening and then as clinically indicated (the same methods must be used throughout the study). LVEF need to be checked for eligibility.
13. Hematology includes: Hemoglobin, hematocrit, RBC, WBC with differential, Mean Corpuscular Volume (MCV) and platelet counts. To be done at screening, then prior to pre-medication and IMP administration on Day 1, Day 8, Day 15 and Day 22 of Cycle 1 and on Day 1 and Day 15 of every subsequent cycle, at the EoT visit and as clinically indicated. If Grade 4 neutropenia, assess ANC every 2-3 days until ANC $\geq 0.5 \times 10^9/L$ and at least weekly thereafter until ANC $\geq 1.0 \times 10^9/L$. Perform direct and indirect coombs tests prior to the first IMP administration.
14. Not required to be repeated prior to Day 1 Cycle 1 if the screening labs were performed within 3 days prior to first IMP administration.

15. Serum chemistry includes: SGOT (AST), SGPT (ALT), bilirubin (total and direct), alkaline phosphatase, lactate dehydrogenase (LDH), fasting glucose, sodium, potassium, magnesium, chloride, calcium, corrected serum calcium, phosphate, uric acid, blood urea nitrogen (BUN), serum creatinine and eGFR (Revised equations for eGFR in Japanese), albumin and total protein. To be done at screening, then prior to pre-medication and IMP administration on Day 1, Day 8, Day 15 and Day 22 of Cycle 1 and on Day 1 and Day 15 of every subsequent cycle, at the EoT visit and as clinically indicated.
16. Coagulation: To be done at screening and then as clinically indicated. Coagulation includes: Prothrombin time (PT) or international normalized ratio (INR) and activated partial thromboplastin time (aPTT).
17. Urinalysis includes: blood, protein, glucose, pH, ketones, bilirubin, leucocytes, nitrites and specific gravity. To be done at baseline, on Day 1 and Day 15 of each cycle, EoT, and if clinically indicated. Quantitative urinalysis will be needed if hematuria is observed or clinically indicated.
18. Pregnancy Test: Women of child bearing potential must have a negative serum pregnancy test result within 7 days prior to first IMP administration and at the EoT visit. Urine test can be used at Day 1 of each subsequent cycle.
19. HBc-Ab, HBs-Ab test: If HBc-Ab and/or HBs-Ab positive at baseline, Hepatitis B Virus (HBV)-DNA test is required prior to registration. If history of HBV infection is suspected, monitoring of HBV-DNA is recommended on Day 1 of each cycle, EoT and if clinically indicated.
20. Once at any time if HBV status unknown before treatment started and to be repeated if clinically indicated.
21. Myeloma-specific Lab Tests: serum electrophoresis, immunoglobulin assay, corrected serum calcium and 24-hour urine collection for Bence Jones protein to be performed at baseline prior to administration, prior to each cycle thereafter and at time of study discontinuation (if last tests were >4 weeks). Serum β 2 microglobulin to be performed at baseline prior to administration, EoT and if clinically indicated. Immunofixation and free light chain tests to be performed at baseline prior to administration, EOT, if CR is suspected and if clinically indicated.
Bone marrow aspiration to be performed to confirm a CR and as clinically indicated. In case of dry-tap, bone marrow biopsy to be performed to confirm CR. Once CR is confirmed at a given time point, a consecutive assessment for immunofixation and free light chain is required.
22. Extramedullary Disease: Baseline to be performed within 21 days prior to study drug administration. If extramedullary disease present at baseline, to be performed approximately every 12 weeks (eg. at Cycle 4, 7, 10). To be performed upon clinical suspicion of progressive disease. This may include computerized tomography (CT) or magnetic resonance imaging (MRI) scan of the abdomen/pelvis, CT or x-ray of the chest, ultrasound of the liver/spleen or abdomen. May be omitted at End of Treatment if conducted within 12 weeks. All imaging will be sent to a central imaging lab.
23. Disease assessments during follow-up period are only required for patients with PR or better who have discontinued study treatment for reasons other than disease progression and have not yet started treatment with another anti-cancer therapy. Patients will be followed every 4 weeks for progression during this period. Disease assessments required every 4 weeks is myeloma-specific lab tests. Extramedullary disease assessment is required approximately every 12 weeks or upon clinical suspicion of progressive disease. All imaging will be sent to a central imaging lab. A bone marrow aspiration and/or biopsy, skeletal survey are only required if clinically indicated to confirm response or progression according to IMWG criteria.
Disease assessments not required once patient starts treatment with another anti-cancer therapy.
24. Skeletal survey and chest X-ray: X-ray to be performed at screening on all patients (the same methods must be used throughout the study). Repeat skeletal surveys are only required as clinically indicated. All imaging will be sent to a central imaging lab.
X-ray skeletal survey should include radiographs of the following: lateral skull; Postero-Anterior (PA) chest; Antero-Posterior(AP) and lateral cervical spine; AP and lateral thoracic spine; AP and lateral lumbar spine; AP pelvis; AP upper extremities, shoulder to elbow, bilateral; and AP lower extremities, hip to knee, bilateral.
Chest X ray: To be performed at screening for assessment of pulmonary disease condition and then as clinically indicated.
25. ADA (Anti-Drug Antibodies): To be performed on Day 1, Day 8, Day 15, Day 22 of Cycle 1 and Day 1 of cycle up to 10 cycles prior to each IMP administration, at the EoT visit and at 60 days (\pm 7 days) after last IMP administration. At 60 days, if patient is positive for ADA or the sample is inconclusive, additional ADA samples are required every 30 days (\pm 7 days) until sample is negative. If ADA is positive at Cycle 10, one additional sampling for ADA evaluation should be collected 3 months later. No further ADA will be collected, even if the 3-month sample is positive.

26. Peripheral blood to be collected on Day 1 of Cycle 1 prior to IMP administration for soluble CD38 analysis.
27. Bone Marrow Aspiration and/or biopsy: Bone marrow aspiration (BMA) to be collected at screening/baseline. In case of dry-tap, bone marrow biopsy to be performed. Repeat bone marrow aspiration and/or biopsy if complete response (CR) is suspected to confirm achievement of response.
28. MRD Assessment: Bone marrow aspiration and/or biopsy to be collected at screening/baseline. Repeat bone marrow aspiration and/or biopsy if CR is suspected.
29. CD38 Receptor Density in bone marrow: Bone marrow aspiration to be performed prior to study drug administration at screening/baseline. See PK flowchart.
30. Cytogenetics/ FISH: Bone marrow aspiration and/or biopsy to be performed prior to study drug administration at screening/ baseline for fluorescence in situ hybridization (FISH) analysis. Probes include those to detect del(17p), t(4;14) and t(14;16).
31. Immune phenotyping (BM): Bone marrow aspiration and/or biopsy to be performed at baseline/screening prior to IMP administration.
32. Immune phenotyping (peripheral blood): To be performed at Day 1 of Cycle 1, Day 1 of Cycle 3 prior to IMP administration and at the EoT visit. Immune phenotyping in bone marrow will be performed by bone marrow sample obtained at the screening/ baseline period.
33. Immune genetic determinants (peripheral blood): includes Killer cell Ig-like receptors (KIR), HLA Typing and Fc γ R genes. To be performed at Day 1 of Cycle 1 prior to IMP administration.
34. Survival status: Patients will also be followed for survival status approximately every 3 months (\pm 14 days) from the date of last IMP administration until death or second cutoff date, whichever comes first. Every effort will be made to follow all patients. If survival follow-up is missed and is not obtained at the time of the scheduled interval, it should be obtained immediately. For subsequent survival follow-up, the patient should be contacted at the original scheduled survival follow-up interval. If the patient is unable to visit the clinical center, the follow-up may be done via phone from the Investigator or designee to the patient or the patient's caregiver or a family member.
35. Adverse Event/Serious AE Reporting: All AEs, including events of new onset as well as worsening of baseline signs and symptoms are to be reported from the signing of the informed consent to 30 days following the last administration of study treatment. After the 30 day follow-up all ongoing related AEs, ongoing SAE/AESIs regardless of relationship and new related AE/SAE/AESIs are to be followed to resolution or stabilization.
36. Post second analysis cut-off period, only AE/SAE reporting will be collected

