9.3 EFFICACY

9.3.1 Criteria for Response

ORR is defined as the proportion of patients with stringent complete response (sCR), complete response (CR), very good partial response (VGPR), and partial response (PR) based on responses as assessed using the International Myeloma Working Group (IMWG) Uniform Response Criteria (see [Appendix C](#)). Response evaluation will be performed on a monthly basis. The best overall response for each patient will be determined by independent adjudication committee.

All responses (sCR, CR, VGPR, PR) should be confirmed on 2 consecutive laboratory efficacy parameters assessments according to study flow-chart (approximately 4 weeks interval). Stable disease (SD) does not require confirmation. Disease progression by paraprotein should be confirmed on within the first 4 weeks after last assessment. Disease progression based on imaging, bone marrow plasma cell percentage, or hypercalcemia (not attributable to any other cause) do not need to be confirmed.

Clinical benefit rate (CBR): defined as the proportion of patients with sCR, CR, VGPR, PR or MR according to IMWG criteria.

Duration of response (DOR): defined as the time from the date of the first response to the date of subsequent progressive disease (PD) or death, whichever happens earlier. In the absence of the confirmation of subsequent disease progression or death before the analysis cut-off date, the DOR will be censored at the date of the last valid assessment performed before the analysis cut-off date or date of initiation of new anticancer treatment, whichever is earlier. DOR is determined only for

patients who have achieved a response of \geq PR. DOR will not be calculated for patients that do not achieve a response.

Overall survival (OS): defined as the time interval from the date of first study treatment administration to death due to any cause. In the absence of the confirmation of death before the analysis cutoff date, OS will be censored at the last date the patient is known to be alive or at the study cutoff date, whichever is earlier.

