12.3.4 Day 15 of Each Cycle

The evaluations below are to be performed prior to IMP administration on Day 15 of each cycle unless otherwise indicated.

- Clinical Examinations:
 - Physical Examination (Cycle 1, 2, 3 only)
 - Weight
 - Vital signs
(to be taken pre-infusion, mid-infusion (when half the volume is administered), and end-infusion on days of IMP administration. If the infusion rate changes because of an infusion-associated reaction, vital signs should be monitored every hour and at the end of the infusion.)
 - AE/ SAE assessment
 - Concomitant Medications
- Laboratory Assessments:
 - Hematology
 - Serum Chemistry
 - Urinalysis: Quantitative urinalysis will be needed if hematuria is observed or clinically indicated.
 - In case of viral reactivation during study treatment (greater than $1 \log_{10}$ IU/mL increase in HBV DNA or reappearance of HBsAg or detection of HBV DNA in patients with resolved infection), ALT and AST will be closely monitored every month up to study treatment discontinuation. HBV DNA to be done as per specialist advice (Phase II part, Subsequent Cycles only).
- PK (refer to [Section 1.7](#) and [Section 1.8](#), up to 10 cycles)
- ADA (Cycle 1 only)

Administration of isatuximab

Isatuximab Safety Labs

12.4 END OF TREATMENT VISIT (TO BE PERFORMED 30 DAYS (+/- 7 DAYS) AFTER THE LAST ADMINISTRATION OF THE INVESTIGATION MEDICINAL PRODUCT)

- Inform to the registration center
- Clinical Examinations:
 - Physical Examination
 - Performance Status (ECOG)
 - Weight
 - Vital signs
 - AE/ SAE assessment
 - Concomitant Medications
- Laboratory Assessments:
 - Hematology
 - Serum Chemistry
 - If history of HBV infection is suspected, perform HBV-DNA test.
 - Urinalysis: Quantitative urinalysis will be needed if hematuria is observed or clinically indicated.
 - Serum Pregnancy Test
- Disease Assessment:
 - Myeloma-specific Lab Tests:
 - M-protein quantification (serum electrophoresis and immunofixation and 24-hour urine collection for Bence Jones protein with urine electrophoresis and immunofixation)
 - Serum free light chain levels
 - Serum β 2-microglobulin
 - Immunoglobulins: IgG, IgA, IgM, IgD and IgE
 - Corrected serum calcium
 - Extramedullary Disease (approximately every 12 weeks, eg. Cycle 4, 7, 10): Required if positive at screening/ baseline as determined by Independent Adjudication Committee. May be omitted at End of Treatment if conducted within 12 weeks.
- PK and ADA (refer to [Section 1.7](#) and [Section 1.8](#))

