Appendix C IMWG Response Criteria

Disease response will be assessed using the updated International Myeloma Working Group Response Criteria (IMWG)(10).

A confirmation assessment within 4 weeks (± 3 days) for disease response evaluation assessments is required in this protocol, including MR.

Table 9 - International Myeloma Working Group Response Criteria

Response	IMWG criteria
sCR	CR as defined below plus: 
Normal FLC ratio andAbsence of clonal cells in bone marrow by immunohistochemistry or 2 – 4 color flow cytometry
CR	
Negative immunofixation on the serum and urine andDisappearance of any soft tissue plasmacytomas and<5% plasma cells in bone marrow.In patients with only FLC disease, a normal FLC ratio of 0.26–1.65 is required.
VGPR	
Serum and urine M-protein detectable by immunofixation but not on electrophoresis or$\geq 90\%$ reduction in serum M-protein plus urine M-protein level <100 mg/24 h.In patients with only FLC disease, $>90\%$ decrease in the difference between involved and uninvolved FLC levels is required.
PR	
$\geq 50\%$ reduction of serum M-protein and reduction in 24 hours urinary M protein by $\geq 90\%$ or to <200 mg/24 hIf the serum and urine M-protein are unmeasurable, a $\geq 50\%$ decrease in the difference between involved and uninvolved FLC levels is required in place of the M-protein criteriaIf serum and urine M-protein are not measurable, and serum free light assay is also not measurable, $\geq 50\%$ reduction in plasma cells is required in place of M-protein, provided baseline bone marrow plasma cell percentage was $\geq 30\%$In addition to the above listed criteria, if present at baseline, a $\geq 50\%$ reduction in the size of soft tissue plasmacytomas is also required
SD	
Not meeting criteria for CR, VGPR, PR or progressive disease

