PD	Increase of $\geq 25\%$ from lowest response value in any one of the following: 
Serum M-component (the absolute increase must be ≥ 0.5 g/dL) and/orUrine M-component (the absolute increase must be ≥ 200 mg/24 h) and/orOnly in patients without measurable serum and urine M-protein, the difference between involved and uninvolved FLC levels. The absolute increase must be >10 mg/dLOnly in patients without measurable serum and urine M-protein and without measurable disease by FLC levels, bone marrow plasma cell percentage (absolute % must be $\geq 10\%$)Definite development of new bone lesions or soft tissue plasmacytomas or definite increase in the size of existing bone lesions or soft tissue plasmacytomasDevelopment of hypercalcemia (corrected serum calcium >11.5 mg/dL) that can be attributed solely to the plasma cell proliferative disorder

All response categories (CR, sCR, VGPR, PR and PD) require two consecutive assessments made at any time before the institution of any new therapy; complete response and PR and SD categories also require no known evidence of progressive or new bone lesions if radiographic studies were performed. VGPR and CR categories require serum and urine studies regardless of whether disease at baseline was measurable in serum, urine both or either. Radiographic studies

are not required to satisfy these response requirements. Bone marrow assessments need not be confirmed. For progressive disease, serum M-component increases of ≥ 1 g/dL are sufficient to define response if starting M-component is ≥ 5 g/dL.

IMWG clarification for coding PD: Clarified that Bone marrow criteria for PD are to be used only in patients without measurable disease by M protein and by FLC levels. Clarified that 25% increase refers to M protein, FLC, and bone marrow results and does not refer to bone lesions, soft tissue plasmacytomas or hypercalcemia. Note the lowest response value does not need to be a confirmed value.

Table 10 - Additional response criteria for specific disease states

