#### **2.1.3 Efficacy endpoints**

Response assessments were to be performed on a monthly basis using IMWG criteria (Rajkumar. 2011) and included:

- M-protein quantification (serum and 24-hr urine)
- Serum free light chain levels
- Corrected serum calcium

In case of plasmacytoma at baseline, radiological evaluations were to be performed every 3 cycles or when clinically indicated (i.e., to confirm a progression).

In case of bone lesions at baseline, bone lesion evaluations were to be performed when clinically indicated or to confirm a response or progression. Bone marrow biopsy/aspiration was to be performed to confirm a sCR or CR.

An independent adjudication committee (IAC) independently assessed clinical response using the IMWG response criteria.

Biological responses ( $\geq$ PR) and progression were to be confirmed on 2 consecutive biological (serum and/or urine M protein) disease assessments. No confirmation was required for radiological assessment.

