#### **2.1.3.2 Secondary efficacy endpoint(s)**

Secondary efficacy endpoints are defined below.

- Duration of Response (DOR) (in weeks): DOR is defined as the time from the date of the first IAC determined response ( $\geq$  PR) that is subsequently confirmed, to the date of first IAC determined PD or death, whichever happens earlier (if reported before the analysis cut-off date or the date of initiation of a new anticancer treatment). If progression and death are not observed before the analysis cut-off date or the date of initiation of new anticancer treatment, DOR will be censored at the earliest of the date of the last valid disease assessment not showing disease progression performed prior to initiation of a further anticancer treatment or the analysis cut-off date. DOR is determined only for patients who have achieved a confirmed response of  $\geq$ PR.
- Clinical benefit rate (CBR): defined as the proportion of patients with sCR, CR, VGPR, PR or MR as BOR according to IMWG criteria, as determined by the IAC.
- Progression free survival (PFS) (in months): defined as the time interval from the date of first isatuximab administration to the date of the first IAC-confirmed disease progression or the date of death due to any cause, whichever comes first. For patients who did not experience IAC-confirmed disease progression and death before the analysis cut-off date or the date of initiation of new anticancer treatment, PFS will be censored at the date of the last valid disease assessment not showing disease progression performed prior to initiation of a further anticancer treatment or the analysis cut-off date, whichever comes first.
- Overall survival (OS) (in months): defined as the time interval from the date of first isatuximab administration to death from any cause. In the absence of the confirmation of death before the cut-off date, OS will be censored at the cut-off date or at the last date the patient is known to be alive, whichever comes first.

- Time to response (TTR) (in weeks): TTR is defined as the time from first dose to first IAC response (PR or better) that is subsequently confirmed.
- Duration of follow-up (DFU) (in weeks): DFU is defined as the time from first dose to last response disease assessment before start of other therapy or cut-off date, whichever comes first.

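### Footnote 21 conflicts with section 12.4 and can waive the only scheduled M-protein sample that would confirm progression, so some progressions may be censored in PFS

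*Protocol*

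**What the plan says.** **Testing schedule.** Protocol section 1.6, footnote 21, asks for serum electrophoresis and the 24-hour urine collection at baseline, then "prior to each cycle thereafter and at time of study discontinuation (if last tests were >4 weeks". The footnote is attached to the myeloma laboratory row of both flowcharts, so it qualifies the mark in the EoT column. Section 12.4 lists for the EoT visit "M-protein quantification (serum electrophoresis and immunofixation and 24-hour urine collection for Bence Jones protein with urine electrophoresis and immunofixation" with no condition on the age of the last tests. Its only omission rule, "May be omitted at End of Treatment if conducted within 12 weeks", concerns extramedullary imaging. Footnote 23 limits disease assessments after EoT to responders (PR or better) who stopped for a reason other than progression.

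**Confirmation.** The texts agree that a second result is needed but not on when:
- Protocol 9.3.1: "Disease progression by paraprotein should be confirmed on within the first 4 weeks after last assessment".
- Appendix C, opening text: "A confirmation assessment within 4 weeks (± 3 days) for disease response evaluation assessments is required in this protocol, including MR".
- Appendix C, below Table 9: "All response categories (CR, sCR, VGPR, PR and PD) require two consecutive assessments made at any time before the institution of any new therapy".
- Phase 2 SAP 2.1.3: biological responses and "progression were to be confirmed on 2 consecutive biological (serum and/or urine M protein) disease assessments", with no time limit.

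**Endpoint.** Phase 2 SAP 2.1.3.2 counts as a PFS event "the first IAC-confirmed disease progression or the date of death due to any cause". Patients without an event are censored at their last valid progression-free assessment before new therapy or the cut-off.

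**The concern.** A paraprotein progression becomes a countable event only through a second sample. For a patient whose dosing stops when progression is first seen, the next scheduled visit is EoT. The footnote drops the M-protein tests there precisely when the previous sample is recent.

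An unconfirmed progression would be censored just before the disease was measured as progressing. That censoring is informative: it removes events from patients who are failing and pushes the Kaplan-Meier curve up. This differs from a patient who leaves without progression, because here progression has been measured once and only its confirmation is missing. PFS is secondary, but the second cut-off exists for the final time-to-event analysis (protocol 6.7.2), and SAP 2.4.4.2 reports its Kaplan-Meier percentiles.

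**Working it through.** The plan states no PFS assumption, event count or median, so there is no figure of its own to reproduce. The check is calendar arithmetic.

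**1. Inputs.** EoT is 30 ± 7 days after the last dose (12.4). Dosing is weekly in Cycle 1 and two-weekly afterwards (6.2.1). M-protein is sampled before each cycle (footnote 21). Four weeks is 28 days, and the Appendix C allowance extends this to 28 + 3 = 31 days. Nominal visit days are assumed; the visit tolerances would shift the results by a few days.

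**2. Days from the progression sample to EoT.** Let the first sample showing progression be day 0 (Day 1 of a cycle, before dosing) and let L be the day of the last dose. EoT then falls on days L + 23 to L + 37, a window of 15 days. The cells count window days under footnote 21.

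| Last dose (L) | EoT day | Day 28 or earlier: waived | Days 29–31: tested | Day 32 or later: tested |
|---|---|---|---|---|
| −14 (Day 15 of previous cycle; Cycle 3 onward) | 9–23 | 15 | 0 | 0 |
| −7 (Cycle 1 Day 22; progression at Cycle 2 Day 1) | 16–30 | 13 | 2 | 0 |
| 0 (dose given on the sample day) | 23–37 | 6 | 3 | 6 |
| +14 (Day 15 of that cycle also given) | 37–51 | 0 | 0 | 15 |

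**3. Does a time limit matter?** Under the 28-day limit, a sample required by footnote 21 is always late. With the 3-day allowance it is in time only on days 29–31. Under the other Appendix C sentence and SAP 2.1.3, a sample after day 28 still confirms if no new therapy has started. Those rules rescue the fourth row and the later part of the second and third. They do not help the first row, where all 15 days are waived and footnote 23 schedules nothing later.

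**4. If section 12.4 is followed.** The EoT sample is taken in every row. In the first row all 15 days fall within 28. In the second, 13 of 15 fall within 28 and all within 31. In the third, 6 of 15 fall within 28 and 9 of 15 within 31. In the fourth, none falls within 31.

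**5. Could other EoT tests confirm instead?** Footnote 21 keeps β2-microglobulin, immunofixation and free light chains at EoT. Appendix C uses free light chains for progression only where serum and urine M-protein are not measurable. Inclusion I 06 requires measurable M-protein, and exclusion E 02 removes patients measurable by free light chains only. These tests therefore do not fill the gap.

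**6. Illustrative size, on assumptions outside the documents.** Suppose PFS is exponential, all events are progressions, and a random fraction f is left unconfirmed. The event hazard falls from λ to (1 − f)λ, so the median is multiplied by 1/(1 − f):
- f = 10%: 1/0.9 = 1.11
- f = 20%: 1/0.8 = 1.25
- f = 30%: 1/0.7 = 1.43

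A simulation of 4,000 trials used N = 36, a true median of 5 months, 28-day visits, a 20-month cut-off, and censoring at the preceding visit. The mean Kaplan-Meier median rose from 5.35 to 6.03, 6.75 and 7.55 months. The ratios are 6.03/5.35 = 1.13, 6.75/5.35 = 1.26 and 7.55/5.35 = 1.41.

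**The case against.** The strongest reply is that the protocol does schedule the sample. Section 12.4 lists it at EoT unconditionally, and 9.3.1 and Appendix C call for a confirming assessment in their own right. A reader might infer from footnote 21 alone that no confirming sample is scheduled, or that the waiver and the confirmation window exclude each other. The documents do not support either. Section 12.4 contradicts the first. The 31-day allowance and the two rules without a day limit contradict the second. What stands is a conflict between footnote and section that leaves sites to choose.

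It can also be said that footnote 21 speaks of leaving the study and uses the term EoT for other tests, so it may not mean that visit. That is fair. But on that reading the footnote provides no M-protein quantification at EoT at all, and the conflict with 12.4 remains.

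A reader might further infer that every such patient is censored. That does not follow, for these reasons:
- Section 11.1.1 lists progression as a reason to stop under the investigator's judgement, so stopping at the first raised value is not automatic.
- Progression by imaging, marrow or hypercalcemia needs no confirmation (9.3.1).
- Death before new therapy or the cut-off still counts.
- The SAP's PFS wording could mean committee adjudication, although SAP 2.1.3 still asks for two consecutive results.
- Protocol 9.3.1 defines PFS by the first assessed progression.
- The SAP's duration of response refers to progression as determined, not confirmed, by the committee, so the effect there is weaker.

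**Conclusion.** The point holds as a conflict that creates a risk. If sites follow footnote 21, a patient whose dosing stops at the first-progression sample (Cycle 3 onward) reaches EoT 9 to 23 days later with the tests waived and nothing scheduled afterwards. The progression may stay unconfirmed and the patient may be censored for PFS. Any resulting bias is upward for PFS and possibly for duration of response.

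The size cannot be derived from the documents. It depends on how many sites follow the footnote, how many patients stop at the first progression sample, and how the adjudication committee treats a single result. The 13% to 41% range shows what 10% to 30% unconfirmed progressions would do under an exponential 5-month median. A reader should not take it as an estimate of bias in this trial.

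The primary ORR test does not depend on confirming progression and is unaffected. PFS is descriptive, with no hypothesis test. The point is worth correcting because the remedy is small, but it does not threaten the trial's main conclusion.

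**What to change.** 1. In footnote 21, delete the parenthetical condition on the age of the last tests, so that it agrees with section 12.4.
2. Add that a first paraprotein progression is followed by a repeat serum and 24-hour urine M-protein before any new anti-myeloma therapy starts, even if study treatment has stopped. Step 1 alone is not enough if a day limit is kept: when Day 15 of the same cycle was dosed, no EoT visit falls within 31 days.
3. Reconcile the confirmation windows in protocol 9.3.1 (4 weeks), Appendix C (4 weeks ± 3 days in one place, any time before new therapy in another) and SAP 2.1.3 (no limit), so that sites and the adjudication committee apply one rule.

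The cost is a text edit in both documents and at most one repeat laboratory test per progressing patient. Section 12.4 already lists that test, so no new procedure is introduced.
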